Subjects will be outpatients who meet the DSM-V criteria for PTSD (acute or chronic, confirmed by the Clinician Administered PTSD Scale [CAPS] and at least moderate severity, defined as score > 33 on the PTSD checklist [PCL-5]) and have at least moderate symptoms of depression (defined by moderate symptoms, or score ≥ 11 on the Quick Inventory for Depressive Symptomatology – Subject Rated [QIDS-SR]) and are 18 to 70 years of age (inclusive). Up to 35 participants will complete the study at the two sites, the Providence VAMC (Providence, RI) and the White River Junction VAMC (White River Junction, VT). Eligible subjects must provide written informed consent, be capable of comprehending the nature of the study, and be considered by the Investigator as likely to comply with the visit schedule. Additional inclusion/exclusion criteria are listed below.

2. Study Design

This study is a prospective, sham-controlled, trial of sTMS delivered to patients who are symptomatic despite ongoing pharmacotherapy for PTSD and mood symptoms. Serial self-report symptom assessments will take place at screening/baseline and weekly during the 4

weeks of the study. The treatment course will comprise a total of 20 double-blind treatment sessions. Treatments windows will be 10 calendar days to complete 5 treatments, with a 40-day window in total to complete 20 treatments. Post-treatment assessment sessions will take place on the last day of treatment, and again 1 month after the final treatment.

All veterans who complete the sham-controlled series will be offered open-label continuation treatment following the same administration structure (i.e., 20 open-label treatment sessions, with 10 calendar days to complete 5 treatments, within a 40-day window for all 20 treatments), with a 1-month, post-treatment visit). Of note, for patients who continue in open-label participation, the 1 final study visit (PT2, below) will occur 1 month after the final open label treatment.

3. Specific Procedures or Treatments

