A. Screening: Patients who call in response to advertisements for the study or are referred by clinicians and meet preliminary demographic eligibility criteria upon phone screen will be invited to the clinic for a screening visit. Participants will also be drawn from clinical and research clinics at participating sites. After providing written informed consent, psychiatric interview and self-report measures will be used to confirm eligibility with regard to diagnosis, past psychotropic treatment history, current health history, and current symptom severity. The requirement for maintenance on a stable regimen of psychotropic medications for 6 weeks prior to baseline and during participation in the course of sTMS will be discussed.

B. Baseline/First Treatment Day: Patients meeting eligibility criteria will return within 2 weeks to begin the treatment protocol. Consent will be reviewed and confirmed with standard-of-practice forms for each institution. If indicated, women will be given a pregnancy test to make sure they are not pregnant. Clinical assessments will be updated (if more than 2 weeks have passed since screening visit), and data regarding functioning and quality of life will be collected with standardized measures. sTMS delivery will be calibrated using standard NeoSync procedures found in the device's user manual.

C. Serial Assessments: In the table below, PT1 refers to the assessment after the final sTMS treatment (i.e., after week 4 of the sham-controlled phase and, if relevant, after week 8 of the open-label phase). PT2 refers to the assessment completed 1 month after the final treatment (sham-controlled or open-label). PT1 and PT2 will include a psychiatric interview with the study PI or their designee. SC= screening visit, BL=Baseline/first treatment day, OL = open-label, with brackets indicating procedures done only in patients participating in the OL continuation phase. End-of-treatment week assessments are listed according to number of weeks of sTMS therapy completed by the time of assessment. * Indicates repeat evaluation at baseline if more than two weeks has passed since screening. Note that psychiatric assessments will occur at SC/BL, PT1, [OL PT1,] and PT2.

Table 1: Serial Assessments

Abbrev:	Assessment Title:	Administered at:
CAPS	Clinician Administered PTSD Scale	SC, BL*, PT1, [OL PT1,] PT2
CTQ	Childhood Trauma Questionnaire	SC, BL*
CGI-S	Clinical Global Impression - Severity	SC, BL*, PT1, [OL PT1,] PT2

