QIDS-SR	Quick Inventory of Depressive Symptoms – Self Report	SC, BL*, Weeks 1-3, PT1, [OL Weeks 5-7, OL PT1,] PT2
PCL-5	PTSD Checklist	SC, BL*, Weeks 1-3, PT1, [OL Weeks 5-7, OL PT1,] PT2
GAD7	7 Item Generalized Anxiety Disorder Scale	SC, BL*, PT1, [OL PT1] PT2
Q-LES-	Quality of Life Enjoyment and Satisfaction	SC, BL*, PT1, [OL PT1] PT2
Q-SF	Questionnaire	
CGI-I	Clinical Global Impression – Improvement	PT1, [OL PT1,] PT2
PGI-I	Patient Global Impression - Improvement	PT1, [OL PT1,] PT2

D. sTMS Treatment Administration: sTMS will be delivered following NeoSync administration guidelines using the device user manual. Acting under the direct supervision of a TMS-credentialed physician, trained sTMS operators will supervise all treatments.

Treatment emergent side effects associated with stimulation (during treatments) and emerging between treatment sessions will be queried on each treatment day and recorded.

E. Serial Imaging: Participants (at Providence VAMC site) found eligible at SC may undergo three MRI scanning sessions during the course of this study. Scans may occur prior to BL/first treatment day and after completing each study phase (i.e., after PT1 and PT1 OL). Scans will be completed at Brown University MRI Facility (MRF) or Providence VAMC; with scanner location remaining consistent for each participant (i.e., a participant BL screened at Brown will undergo PT1 scan at Brown, not PVAMC). Eligible participants will be scheduled to arrive at either facility 1 hour prior to MRI start time. At that time research staff will review MRI safety and study procedures, and discuss any changes in mood, sleep, and/or medication since their last visit. Additionally, participants will be asked to complete the Perceived Stress Scale prior to entering the scanner. Once in the magnet, research staff will ensure that the participant is comfortable, able to view the task screen, and has been provided the necessary instructions regarding communication with research staff during the scan (e.g., using emergency squeeze ball). After each scan, the participant will be queried about their experience in the scanner to assess for anxiety and/or discomfort.

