We aim to maximize power through collaborative analyses including data collected from the two sites of the study. De-identified data will be shared for final analyses. At least 20 subjects will be completed in total. The sample size for this pilot controlled study is based on estimations regarding the appropriate amount of information required to inform next steps in trial design rather than on statistical significance calculations for any primary safety or efficacy endpoint. Previous studies of different TMS parameters for PTSD (without comorbid MDD) have utilized sample sizes of ~ N = 20. By employing a comparable sample size we anticipate having sufficient power to detect significant differences between baseline and endpoint. This sample size will be adequate to determine the appropriate sample size for a subsequent trial.

For the primary efficacy endpoint, we will analyze change in total scores on both PCL-5 scores from baseline to end point PT1. Categorical response (empirically defined as 50% decrease from pre-treatment baseline) and remission (below threshold score, per published standards for each scale) will be calculated for each scale, and these will be reported in a descriptive manner for the sample. Secondary efficacy endpoints will utilize pre- and post-treatment scores on the self-report scales and CAPS. Open-label results, potentially informing issues related to duration of treatment, will be reported descriptively.

IV. Material Inducements

Participants will be offered payments in the form of gift cards, for completion of three milestones in the study: \$25 giftcard for completion of all baseline procedures, \$25 giftcard for completion of all PT1 procedures, and \$50 giftcard for completion of PT2 procedures. There is a maximum total payment of \$100 to offset time and travel expenses incurred as a result of participation in the research assessments that are not standard of care for non-research patients who undergo sTMS therapy. Participants who undergo open-label treatment will receive an additional \$25 for completing OL PT1 procedures, bringing the maximum total of \$125

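### The primary PCL-5 change score has no stated active-sham contrast or baseline covariate and ignores the Week 1-3 scores, and PT1 is undefined for participants who stop early

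*Combined protocol and SAP*

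**What the plan says.** Section III.4 (Power Calculations and Data Analysis) gives the primary efficacy endpoint as "change in total scores on both PCL-5 scores from baseline to end point PT1". For the rest, "Secondary efficacy endpoints will utilize pre- and post-treatment scores on the self-report scales and CAPS"; response, remission and open-label results are descriptive. No model, covariate, analysis set or missing-data rule appears there or elsewhere. Numbers of participants are given only as completers (III.1, III.4, VI.1).

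Table 1 schedules the PCL-5 at "SC, BL*, Weeks 1-3, PT1, [OL Weeks 5-7, OL PT1,] PT2". The asterisk means that the baseline measure is repeated only if more than two weeks have passed since screening.

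On timing, III.2 (Study Design) says "Post-treatment assessment sessions will take place on the last day of treatment" and allows five sessions to take 10 calendar days, "with a 40-day window in total to complete 20 treatments". III.3.C (Serial Assessments) says "PT1 refers to the assessment after the final sTMS treatment (i.e., after week 4 of the sham-controlled phase". It adds: "End-of-treatment week assessments are listed according to number of weeks of sTMS therapy completed by the time of assessment".

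**The concern.** The trial is sham-controlled, so the result of interest is presumably the active-sham difference at the end of the blinded course. The primary sentence does not state that comparison, and the power sentence in III.4 refers to baseline versus endpoint. Three things follow.

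- A raw change score subtracts baseline but does not adjust for it as a covariate, which wastes precision in a trial of 20 to 35 people.
- For someone who stops early, PT1 could be the score on the last treatment day, a score at the week-4 time, or nothing. The first counts a score that has had less time to fall. The last leads to a completer analysis. With no rule, the choice can be made after the data are seen.
- The Week 1-3 scores carry information about those who stop, and no stated analysis uses it.

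At stake is a modest error in the estimate and the residual SD that this pilot is meant to hand to the next trial.

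**Working it through.** **Nothing to reproduce.** III.4 says that the sample size does not rest on a significance calculation. The documents give no SD, drop-out rate, correlation, effect size or allocation ratio. Apart from the day count, every number below rests on stated assumptions.

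**1. When PT1 falls.** Take the first treatment as day 1. At five weekday sessions a week (VI.3.C), session 20 falls on day 26 for a Monday start and day 28 for any other start. III.2 allows up to day 40. At 10 days per five sessions, session 15 may fall as late as day 30. A calendar window such as days 26-40 would therefore admit, as PT1, the score of someone who stopped after session 15 on day 28, or a slow completer's Week 3 score. Sessions completed is the safer index, and III.3.C already uses weeks of therapy completed.

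**2. Baseline adjustment.** With equal SD at both times and baseline-to-PT1 correlation r:

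- variance of raw change = 2 × SD² × (1 − r)
- residual variance after ANCOVA = SD² × (1 − r²)
- ratio = (1 + r)/2 = 0.65, 0.75, 0.85 for r = 0.3, 0.5, 0.7, or 35%, 25%, 15% less variance.

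For a true difference of 0.8 SD, two-sided 0.05, 10 per arm and no loss, power rises from 30% to 42%, 40% to 50% and 59% to 66%.

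**3. Last-treatment-day score counted as PT1.** Assume a linear fall F, and stops spread evenly after weeks 1, 2 and 3 and unrelated to outcome. The mean share of the fall still to come is (3/4 + 2/4 + 1/4)/3 = 1/2. With loss p in each arm, and positive values counting against active:

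bias = ½ × (p_active × F_active − p_sham × F_sham)

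- Loss 10% v 30%, fall 10 in both arms: ½ × (1 − 3) = −1.0 point. Falls of 5 and 20 give −0.5 and −2.0.
- Equal 20% loss, falls 20 v 10: ½ × (4 − 2) = +1.0, towards no effect. Falls 15 v 10: ½ × (3 − 2) = +0.5.

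Simulation of the 20 v 10 case (correlation 0.8) gave +1.09, +0.96 and +1.05 when poor improvers leave, leaving is unrelated to outcome, and good improvers leave. Completer ANCOVA stayed between −0.06 and +0.13. The formula assumes that every stopper has a last-day score; if only half do, the −1.0 becomes −0.64.

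**4. Unequal loss, no true effect.** Assumptions: 14 per arm, SD 14, first-order autoregressive correlation 0.8 / 0.9, fall of 10 in both arms, loss 10% active and 30% sham (1.4 v 4.2 people). There were 8,000 simulated trials per scenario; Monte Carlo error was about 0.05-0.07. Bias in points:

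| Who leaves | Raw change, completers | ANCOVA, completers | Last-day PT1 | Likelihood model |
|---|---|---|---|---|
| Poor improvers | +2.37 / +1.87 | +1.55 / +1.51 | −1.45 / −1.24 | −0.01 / −0.01 |
| Unrelated | +0.10 / +0.07 | +0.03 / +0.03 | −1.03 / −1.03 | −0.02 / −0.01 |
| Good improvers | −2.20 / −1.75 | −1.52 / −1.49 | −0.72 / −0.94 | +0.02 / +0.01 |

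At 10% v 20% loss, ANCOVA is at most 0.77 and last-day 0.74 in size. For scale, at an equal 20% loss with poor improvers leaving, the sampling SD of completer ANCOVA is 5.43 / 4.41, so 1.55/5.43 = 0.29 and 1.51/4.41 = 0.34. For raw completer change, 2.37/6.14 = 0.39 and 1.87/4.64 = 0.40.

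**5. Precision, equal 20% loss.** Baseline adjustment alone lowers the standard error of the raw change by 4-13%; the repeated-measures model lowers it by 3-15%. Against completer ANCOVA, the model ranges from 2% larger to 4% smaller.

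**6. Leaving that depends on unseen scores (10% v 30%).** If it depends on the PT1 score itself: ANCOVA +2.58 / +2.25, model +1.94 / +1.53. If it depends on change after week 3: ANCOVA +1.24 / +1.09, model +1.50 / +1.22, so the model is worse. A PT1 score from half of the stoppers cuts the model's bias to +0.67 / +0.51 and +0.53 / +0.42.

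**7. Feasibility.** In 4,000 trials, at least 99.9% of unstructured REML fits converged. With degrees of freedom set to the number of PT1 scores minus 4, the 5% test rejected 4.9-5.7% of the time, including at 10 per arm.

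**The case against.** The strongest reply is that this is a pilot that disclaims formal powering, that its text is silent rather than wrong, and that every bias above comes from invented inputs. Much of that stands. A change from baseline to PT1 is an endpoint that a repeated-measures model can also estimate. The documents give no reason to expect a large difference in loss: VI.3.A reports no significant active-sham difference in side effects in an earlier trial (headache 21.4% v 19.2%). The open-label phase ("All veterans who complete the sham-controlled series will be offered open-label continuation treatment") and the PT1 payment in section IV both encourage staying. An unstructured model on 20 to 35 people adds little precision over completer ANCOVA and can do worse when leaving depends on unseen scores.

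Three things survive it. Baseline adjustment uses data already collected and improves on a raw change at almost no cost. A literal reading of III.2 would count an early stopper's last-day score as PT1, which is avoidable. And III.4 does name a primary efficacy endpoint, so the comparison should be stated.

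A reader might infer that the plan prescribes a completer analysis. It does not: the completer counts are enrolment targets. Nor do III.2 and III.3.C contradict each other for a full course. They agree there and are silent only on those who stop.

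**Conclusion.** The point holds as a moderate, cheaply mended gap. The primary analysis lacks a stated contrast, a baseline covariate and a PT1 rule for early stoppers, and leaves the weekly scores unused. The surest gain is baseline adjustment: 15-35% less variance for assumed correlations of 0.7 down to 0.3. Counting last-day scores as PT1 biases the difference when loss differs between arms, and under equal loss when there is a true effect (about 1 point towards no effect for 20% loss and falls of 20 v 10). This supposes that stoppers' scores would have gone on falling as the others' do. Completer analysis is biased when loss differs and is related to outcome.

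Under the main assumptions the ANCOVA and last-day biases are at most about a third of a sampling SD (about 0.4 for raw completer change), and they roughly halve at 10% v 20% loss. Two stronger readings are not supported: that the trial's result would be invalid, since the documents show nothing that points to large unequal loss; and that the repeated-measures model brings a large gain in precision. The opposite comfort, that equal loss makes every approach safe, fails for last-day scoring if sTMS works, as section II hypothesises.

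**What to change.** Amend III.4 as follows.

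1. Make the primary analysis the active-minus-sham difference in PCL-5 at PT1, adjusted for baseline PCL-5 and site, among all allocated participants who start treatment, in the allocated arm.
2. Define baseline as the last PCL-5 before the first session: the BL score if taken, otherwise the screening score.
3. Index scores by sessions completed. PT1 is the score taken after session 20. A score taken at an early stop goes to the nearest of Weeks 1-3 (5, 10 or 15 sessions) and is never PT1, whatever the day; a scheduled Week 3 score is never PT1. From those who stop, attempt a separate PCL-5 self-report at the planned PT1 time (a stated day range within the 40-day window, before any open-label session) and use that as PT1. This decides only which score counts and changes no treatment.
4. Include Weeks 1-3 through a likelihood-based (REML) repeated-measures model: arm, visit, arm-by-visit, baseline by visit, site by visit, unstructured covariance and a named small-sample degrees-of-freedom method. Only if that fails to converge, use a heterogeneous first-order autoregressive covariance with small-sample-corrected robust variance. Keep completer ANCOVA as a sensitivity analysis, and add a shift analysis (stoppers' predicted PT1 score 0, 5 and 10 points worse, each arm separately).
5. Report numbers allocated, started and completed by arm.

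The cost is SAP wording, slightly more analysis work and one self-report attempt per stopper. The model gives little precision beyond completer ANCOVA and no protection if leaving depends on unseen scores, where it can be worse; the follow-up attempt and the shift analysis are there for that reason.

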(inclusive of acute phase and open-label inducements). Additionally, participants who undergo serial MRI imaging will receive an additional \$50 at each scanning session. There is a maximum total payment of \$150 for completing 3 serial MRI sessions. Thus, participants that complete all primary study procedures and serial imaging procedures may receive a maximum of \$275. Payments may occur via gift cards or EFT.

V. Training of Research Personnel

All research staff will receive study specific training from their site PI prior to their involvement in the study, and all staff will receive device-specific training from NeoSync. Research staff meetings will be scheduled as needed for further training, especially if the protocol is amended. Study PIs will be available to research staff by phone and email to answer any study related questions. Study PIs or their designees will train and supervise research assistants to process and analyze the research data. Study PIs will be responsible for documentation of all training that will be placed in the study's regulatory files. Study PIs or providers with experience in neuromodulation will supervise delivery of sTMS during the study.

VI. Human Participants

1. Participant Population

Up to 35 male and female subjects , age 18 to 70 years, who are suffering from PTSD and comorbid depressive symptoms, will complete the study.

Inclusion Criteria:

- (1) To ensure subjects can safely receive sTMS, eligible subjects must meet all established screening criteria for safety during MRI (magnetic resonance imaging). These are conservative measures require a patient not having the following (unless MRI-safe): Cardiac pacemaker, implanted device (deep brain stimulation) or metal in the brain, cervical spinal cord, or upper thoracic spinal cord;
- (2) Outpatients 18-70 years of age (inclusive);
- (3) Meet DSM-V criteria for PTSD (acute or chronic) at the time of the screening and/or baseline visit; AND report at least moderate symptom severity of depressive symptoms. Participants with bipolar II or otherwise unspecified, who are currently in a depressed episode, will be eligible to participate;
- (4) Have a baseline score of “Moderately Ill” or worse on the CGI-S;

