- (5) Be on a stable psychotropic regimen for at least 6 weeks prior to baseline, or no psychotropic medication at all (for at least 6 weeks prior to baseline), and be willing to maintain the current regimen and dosing for the duration of the study (unless medically necessary to make changes with notification of research staff);
- (7) If female and of child bearing potential, agree to use an acceptable method of birth control for the duration of the study treatment period;
- (8) Be willing and able to comply with all study related procedures and visits;
- (9) Be capable of independently reading and understanding patient information materials and giving written informed consent.

Exclusion Criteria:

Subjects will be excluded from participation if they meet any of the following:

- (1) Are pregnant or lactating or planning to become pregnant within the next three months;
- (2) Have a lifetime history of loss of consciousness due to head injury for greater than 10 minutes, or any lifetime history of loss of consciousness due to a head injury with documented evidence of brain injury (including brain atrophy);
- (3) Current (or past if appropriate) significant neurological disorder, or lifetime history of a) seizure disorder b) primary or secondary CNS tumors c) stroke or d) cerebral aneurysm;

- (4) Unstable medical illness, or, in the opinion of the investigator, significant absence of appropriate medical care;
- (5) Current Axis 1 primary psychotic disorder, or bipolar I disorder, active moderate/severe substance use disorders (within the last month, excluding nicotine/caffeine). Veterans on stable (>3 months), monitored opiate agonist therapy may be included at the investigator's discretion;
- (6) Past failed treatment with rTMS or ECT; any past treatment with deep brain stimulation or vagus nerve stimulation;
- (7) Have active suicidal intent or plan as detected on screening assessments, or in the Investigator's opinion, is likely to attempt suicide within the next six months;
- (8) Demonstrate the presence of any other condition or circumstance that, in the opinion of the investigator, has the potential to prevent study completion and/or to have a confounding effect on outcome assessments.
- (9) Inability to obtain EEG of sufficient quality and duration that can be processed for use to calibrate the study device.

2. Recruitment and Consent Procedures

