Potential participants will be recruited through advertisements in the community. Announcements to hospital and community clinicians will be made to facilitate referrals. Research assistants will provide preliminary screening with callers who express interest. Written informed consent will take place as described above, during the screening visit.

3. Potential Risks to Participants

A. Risk of side effects from sTMS treatments: The U.S. Food and Drug Administration has designated this device as a “non-significant risk device” in MDD patients, and in the largest sTMS trial to date for MDD, there were no statistically significant differences in side effects between active and sham sTMS (Leuchter et al., 2015). The most commonly side effect reported was headache (21.4% in active sTMS, 19.2% in sham sTMS). Over-the-counter pain medications such as acetaminophen or ibuprofen may be helpful for reducing discomfort associated with sTMS. Because sTMS remains investigational, study staff will assess subjects' well being and functioning before and after each treatment to minimize the risk of experiencing these or any other side effects.

B. Risk of Worsening PTSD/Depression Symptoms or Lack of Improvement: Risks associated with participation in this trial include possible lack of positive response to sTMS treatment. Worsening of PTSD/Depressive symptoms is also a risk. There is no guarantee that the treatment will lead to improvement of symptoms. During the course of sTMS treatments or after finishing the final session in an sTMS treatment series, symptoms may worsen. The research staff will evaluate subjects at every sTMS treatment session, and the study physician will be available at all times to ensure that participation in this research continues to be safe and reasonable for them.

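### Depressed bipolar II and unspecified bipolar patients may enrol, but mood elevation is not a named risk, no scheduled scale measures it, and no query or interview is specified to ask about it.

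*Combined protocol and SAP*

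**What the plan says.** **Who may enrol.** Inclusion criterion (3) in section VI.1 states: "Participants with bipolar II or otherwise unspecified, who are currently in a depressed episode, will be eligible to participate". Exclusion criterion (5) removes bipolar I but not other bipolar disorder. Inclusion criterion (5) accepts a stable regimen "or no psychotropic medication at all (for at least 6 weeks prior to baseline"), whereas section III.2 describes the patients as "symptomatic despite ongoing pharmacotherapy for PTSD and mood symptoms".

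**Which risks are named.** Section VI.3 (Potential Risks) covers side effects, with headache the most common; worsening or non-response; burden; confidentiality; and unknown risks. On psychiatric change, VI.3.B says: "Worsening of PTSD/Depressive symptoms is also a risk". The sTMS safety evidence cited in VI.3.A and VI.3.E comes from major depressive disorder.

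**What is measured and asked.**
- Table 1 lists CAPS, CTQ, CGI-S, QIDS-SR, PCL-5, GAD7, Q-LES-Q-SF, CGI-I and PGI-I.
- Section III.3.D provides a side-effect query on every treatment day.
- Section III.3.C adds: "PT1 and PT2 will include a psychiatric interview with the study PI or their designee". There is also an interview at OL PT1 for those who continue to open label.
- The section on protection against risks (part A) relies on spontaneous report to identify adverse effects of sTMS.
- Section III.3.E has staff discuss changes in mood and sleep before an MRI scan. Scanning is optional and at Providence only.

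**The concern.** Bipolar II is by definition a disorder with hypomanic episodes. Mood elevation is therefore foreseeable in this subgroup whether or not sTMS causes it, and the general statement about unknown risks does not cover a foreseeable one. Safety findings from major depressive disorder do not speak to it either.

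The difficulty is one of detection. A patient becoming hypomanic may feel better and volunteer nothing. Where the protocol states what staff should watch for, it is deterioration or adverse events, so a switch could be read as response. At stake are late recognition in a patient who may be taking no medication, and an event that goes unrecorded. The first bears on patient protection. The second leaves the safety half of aim i incomplete for these patients and passes less information to the home-use trials that aim iii is meant to inform.

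**Working it through.** The plan gives no figure to reproduce. The check compares the texts and counts contacts from the schedule.

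**1. Is mood elevation addressed anywhere?**

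| Place in the protocol | What it covers | Directed at mood elevation? |
|---|---|---|
| VI.3, Potential Risks | Headache, worsening or non-response, burden, confidentiality, unknown risks | Not named |
| Table 1 | Nine scales: PTSD, childhood trauma, depression, anxiety, quality of life, global impressions | No mania or hypomania scale |
| III.3.D, treatment-day query | Side effects during and between sessions | Content not given |
| III.3.C, interviews | Psychiatric interview | Content not given |
| VI.3.A, per-session check | General state and functioning | Not specified |
| Protection against risks, part A | Spontaneous report of side effects | Not specified |
| VI.5, Risk-Benefit Ratio | Clinic contact five days per treatment week, looking for worsening and adverse events | Not specified |
| III.3.E, pre-MRI discussion | Changes in mood and sleep | Nearest match, but general and optional |

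**2. Existing occasions on which it could be asked.** Inputs: 20 blinded sessions and, for those who continue, 20 open-label sessions (III.2); interviews at PT1, OL PT1 and PT2 (III.3.C).
- Treatment-day queries: 20 in the blinded phase; 20 + 20 = 40 with open label.
- Interviews after baseline: PT1 + PT2 = 2; PT1 + OL PT1 + PT2 = 3 with open label.
- Occasions for which a question on mood elevation is specified: 0.

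**3. Longest span between formal interviews.** III.3.B says: "Patients meeting eligibility criteria will return within 2 weeks to begin the treatment protocol". Table 1 assessments marked for baseline are repeated only if more than two weeks have passed since screening. Treatment then runs "with a 40-day window in total to complete 20 treatments". If the baseline interview is not repeated, screening to PT1 can reach 14 + 40 = about 54 days. This is an upper limit on the gap between interviews, not a detection interval, because 20 treatment-day contacts fall inside it.

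**4. Pre-MRI discussions.** Scans are placed before baseline, after PT1 and after OL PT1, so a scanned Providence participant has at most 3. None is placed between the first session and PT1. White River Junction participants have 0.

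**5. Number of askings under the proposed fix.** On timing, III.2 says: "Post-treatment assessment sessions will take place on the last day of treatment, and again 1 month after the final treatment". PT1 therefore coincides with the 20th session and is not counted again.
- Blinded phase: 20 + 1 (PT2) = 21.
- With open label, assuming OL PT1 likewise falls on the last open-label session: 20 + 20 + 1 (PT2) = 41.

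**The case against.** The strongest reply is that wording is missing, not monitoring. Patients are evaluated at every session and overseen by research psychiatrists. Staff meet to review ongoing data, the site investigator reviews data within a week, and information about the therapy is shared with the prescribing psychiatrist. The query and interviews are not confined to depression or PTSD, and a psychiatrist interviewing a patient with known bipolar II may well ask about elevation. A short pilot protocol need not script that. Bipolar I is excluded, exclusion (8) gives the investigator discretion, and risk factors are screened at entry. The documents report no mood elevation with sTMS, and the trial might enrol no bipolar patient. Asking everyone up to 41 times could look out of proportion to a problem in one subgroup.

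Much of this stands. The general monitoring is substantial and could find a switch; the query and interview content is not given and may already cover it; and the size of the risk is unknown. What does not follow is that the gap is closed. The exclusions and screening act at entry, and none of the later safeguards is stated to look for elevation. Frequent contact helps less when the event can pass for improvement and nobody is told to ask. As for asking everyone, a question put in both arms gives a sham rate against which to read positive answers.

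**Conclusion.** The concern holds as a minor point. The protocol enrols a group with a foreseeable adverse mood state, does not name that state as a risk, does not measure it, and specifies no enquiry directed at it. On the schedule, 20 treatment-day queries and 2 interviews in the blinded phase (40 and 3 with open label) carry no specified question about it.

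Frequency cannot be estimated: neither the bipolar share among the up to 35 completers nor a switch rate is given. The conclusion assumes that the undisclosed query and interview content does not already include such a question; if it does, the remedy reduces to saying so. It concerns the protocol text only and makes no claim about what participants are told at consent. The primary PCL-5 endpoint is not directly affected.

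**What to change.** 1. In section VI.3.B, name mood elevation or hypomania as a risk.
2. In section III.3.D, add one directed question to the treatment-day query for all participants in both arms, for example: *Since the last visit, have you had unusually high or irritable mood with more energy or less need for sleep?* Ask it first before session 1, to fix each participant's starting point, and again at PT2 to cover the month since the final treatment.
3. In part A of the section on protection against risks, state that adverse effects are identified by this query as well as by spontaneous report, that the study physician reviews positive answers, and that confirmed elevation is recorded as an adverse event.

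**Cost.** One question on about 21 occasions per participant, or about 41 with open label, at visits that already take place. No new instrument, visit or staff is needed, since a study physician is already on call throughout. Some false positives are likely, because irritability or ordinary improvement can be reported as elevation; physician review before anything is recorded limits this. One gap remains: a switch during the follow-up month would not be found by this question until PT2.
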